8.3.2 DEFINITION OF SERIOUS ADVERSE EVENTS

An SAE is defined as an event that results in death, is life-threatening, results in inpatient hospitalization or prolongation of existing hospitalization, results in persistent or significant disability/incapacity, results in a congenital anomaly/birth defect, or may jeopardize the subject's health and may require medical or surgical intervention to prevent one of the other outcomes listed.

8.3.3 CLASSIFICATION OF AN ADVERSE EVENT

No text is to be entered in this section; rather it should be included under the relevant subheadings below.

8.3.3.1 SEVERITY OF EVENT

For adverse events (AEs) not included in the protocol defined grading system, the following guidelines will be used to describe severity.

- **Mild** – Events require minimal or no treatment and do not interfere with the participant’s daily activities.
- **Moderate** – Events result in a low level of inconvenience or concern with the therapeutic measures. Moderate events may cause some interference with functioning.
- **Severe** – Events interrupt a participant’s usual daily activity and may require systemic drug therapy or other treatment. Severe events are usually potentially life-threatening or incapacitating. Of note, the term “severe” does not necessarily equate to “serious”.

8.3.3.2 RELATIONSHIP TO STUDY INTERVENTION/EXPERIMENTAL MANIPULATION

All adverse events (AEs) will have their relationship to study procedures, including the intervention, assessed based on temporal relationship. The degree of certainty about causality will be graded using the categories below.

- **Related** – The AE is known to occur with the study procedures, there is a reasonable possibility that the study procedures caused the AE, or there is a temporal relationship between the study procedures and the event. Reasonable possibility means that there is evidence to suggest a causal relationship between the study procedures and the AE.
- **Not Related** – There is not a reasonable possibility that the study procedures caused the event, there is no temporal relationship between the study procedures and event onset, or an alternate etiology has been established.

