7.2 PARTICIPANT DISCONTINUATION/WITHDRAWAL FROM THE STUDY

Participants are free to withdraw from participation in the study at any time upon request.

An investigator may discontinue a participant from the study for the following reasons:

- Lost-to-follow up; unable to contact subject
- Participant withdraws consent for further participation and/or data use.
- Safety concerns: any SAE or AE judged related to participation that warrants removal, per the Data and Safety Monitoring Plan and IRB reporting rules.
- Ineligibility discovered post-enrollment, duplicate enrollment, or other protocol violations that compromise data integrity.
- Investigator decision that continued participation poses undue burden or risk (e.g., credible threats of harm), consistent with IRB policies.

The reason for participant discontinuation or withdrawal from the study will be recorded on a dedicated Case Report Form (CRF). Participants who withdraw or are discontinued after randomization will not be replaced; enrollment continues until the target sample size is reached.

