8.3.4 TIME PERIOD AND FREQUENCY FOR EVENT ASSESSMENT AND FOLLOW-UP

The occurrence of an adverse event (AE) or serious adverse event (SAE) may come to the attention of study personnel during study appointments.

All AEs, not otherwise precluded per the protocol, will be captured on the appropriate case report form (CRF). Information to be collected includes event description, time of onset, assessment of severity,

relationship to study procedures (assessed only by those with the training and authority to make a diagnosis), and time of resolution/stabilization of the event. All AEs occurring while on study will be documented appropriately regardless of relationship. All AEs will be followed to adequate resolution.

Any medical or psychiatric condition that is present at the time that the participant is screened will be considered as baseline and not reported as an AE. However, if the study participant's condition deteriorates at any time during the study, it will be recorded as an AE.

Changes in the severity of an AE will be documented to allow an assessment of the duration of the event at each level of severity to be performed. Documentation of onset and duration of each episode will be maintained for AEs characterized as intermittent.

The study coordinator will record events with start dates occurring any time after informed consent is obtained until 7 (for non-serious AEs) or 30 days (for SAEs) after the last day of study participation. At each study visit, the investigator will inquire about the occurrence of AE/SAEs since the last visit. Events will be followed for outcome information until resolution or stabilization.

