8.4.1 DEFINITION OF UNANTICIPATED PROBLEMS

This protocol uses the definition of Unanticipated Problems as defined by the Office for Human Research Protections (OHRP). OHRP considers unanticipated problems involving risks to participants or others to include, in general, any incident, experience, or outcome that meets all of the following criteria:

- Unexpected in terms of nature, severity, or frequency given (a) the research procedures that are described in the protocol-related documents, such as the Institutional Review Board (IRB)-approved research protocol and informed consent document; and (b) the characteristics of the participant population being studied;
- Related or possibly related to participation in the research (“possibly related” means there is a reasonable possibility that the incident, experience, or outcome may have been caused by the procedures involved in the research); and
- Suggests that the research places participants or others at a greater risk of harm (including physical, psychological, economic, or social harm) than was previously known or recognized.

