9.4.4 SAFETY ANALYSES

N/A

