10.1.6 SAFETY OVERSIGHT

[name], the PI, has the responsibility for assessing adverse events (AEs) and serious adverse events (SAEs) and the ultimate responsibility for all data and safety monitoring. She will conduct weekly reviews of any problems related to quality of data collection, transmission, or analyses and of any AEs and SAEs that occurred in the past week. Further, she will conduct annual reviews of SAEs associated with renewal of IRB approval.

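### Relatedness in 8.3.3.2 can be met by timing alone and its two categories overlap, while the AE definitions conflict and no safety summary by arm is planned

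*Combined protocol and SAP*

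**What the plan says.** - **8.3.3.2, basis.** Every AE has its "relationship to study procedures, including the intervention, assessed based on temporal relationship".
- **8.3.3.2, Related.** Three conditions are joined by an or: the event is known to occur with the procedures, there is a reasonable possibility of causation, "or there is a temporal relationship between the study procedures and the event".
- **8.3.3.2, Not Related.** Again three alternatives: no reasonable possibility, no temporal relationship, "or an alternate etiology has been established".
- **8.4.1.** For unanticipated problems, possibly related means that "there is a reasonable possibility that the incident, experience, or outcome may have been caused by the procedures involved in the research".
- **AE definitions.** Section 8.3.1 requires an AE to be unexpected, related or possibly related, and indicative of greater risk than was known. Section 8.2 counts unfavourable effects whether or not they are thought related. Section 8.3.4 has all AEs on study documented whatever their relationship.
- **Exposure.** Both arms have visits at Day 1, Day 92 and about Day 175 (1.3) and a Fitbit week (8.1). STEPS participants also have the app from one week after baseline. The schedule in 1.3 marks a control intervention at Day 8-91 and Day 92.
- **Blinding.** Section 6.3 says that neither participants nor research staff can be blinded.
- **Analysis.** The entry under "SAFETY ANALYSES" (9.4.4) is N/A.

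**The concern.** A causality rule should give one answer per event. This one can give two. Take an appendicitis admission in week 5 of STEPS. It falls within the intervention period, so it is Related. It has another established cause, so it is Not Related. Under 8.4.1 it would not count as related unless there were a reasonable possibility that the research caused it.

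The label is used elsewhere. Section 7.2 lists "any SAE or AE judged related to participation that warrants removal" among the reasons for discontinuing a participant from the study, and 8.3.1 makes relatedness a condition of being an AE at all. If events are filtered through an ambiguous label applied by staff who know the arm, the safety record depends partly on who classified the event.

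The usual safeguard is a count of all events by arm, whatever the attribution. With 9.4.4 at N/A there is none. Yet 2.3.1 names physical activity as a source of risk in STEPS, and 2.3.3 states that the risks are small.

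**Working it through.** The plan gives no event rate, relatedness share or time window, so there is no figure of its own to reproduce.

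**1. Do the categories exclude each other?** Let K = known to occur with the procedures, R = reasonable possibility, T = temporal relationship, A = alternate etiology. As written:

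- Related = K or R or T
- Not Related = (not R) or (not T) or A

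Related fails only when K = R = T = 0, which is 2 of 16 combinations. Not Related fails only when R = T = 1 and A = 0, also 2 of 16. So 16 − 2 − 2 = 12 combinations satisfy both categories and none satisfies neither.

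With T = 1 there are 8 combinations. All 8 are Related. Only the 2 with R = 1 and A = 0 escape Not Related, so 8 − 2 = 6 satisfy both. These are counts of logical cases and do not estimate how often such events occur.

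**2. Against 8.4.1.** The combination T = 1, R = 0 is Related under 8.3.3.2. Under 8.4.1 it is not even possibly related through timing, because that section asks for a reasonable possibility of causation.

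**3. Could the timing test favour one arm?** Assumptions, none of them in the documents: equal and uniform event onset in both arms over Day 1-182 (Day 175 plus the 7-day AE collection period in 8.3.4), and an event meets the timing test if it falls on a procedure day or within w days after one. Control procedure days are 1-7, 92 and 175. STEPS adds Days 8-91.

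| w (days) | Control | STEPS | Ratio |
|---|---|---|---|
| 0 | 9/182 = 4.9% | 93/182 = 51.1% | 10.3 |
| 7 | 30/182 = 16.5% | 107/182 = 58.8% | 3.6 |
| 30 | 76/182 = 41.8% | 130/182 = 71.4% | 1.7 |
| 60 | 136/182 = 74.7% | 160/182 = 87.9% | 1.2 |
| 90 or more | 100% | 100% | 1.0 |

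If the control intervention marked at Day 8-91 in 1.3 counts as a study procedure, the two arms are equal at every w. The shares are also upper limits for the Related label, since step 1 shows that most such events may be labelled Not Related instead.

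**4. AE definitions side by side.** If 8.3.1 is applied, every AE is at least possibly related, so the Not Related grade in 8.3.3.2 has little or nothing to apply to, and the instruction in 8.3.4 to document AEs whatever their relationship has little effect. If 8.2 is applied, unrelated events are AEs. A count of AEs differs between the two readings, and under 8.3.1 it is already filtered by the label in question.

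**5. Would a table by arm be informative with few events?** With 0 events in n participants, the one-sided 95% upper bound is 1 − 0.05^(1/n). For n = 164/2 = 82 randomized it is 3.6%; for n = 136/2 = 68 completers (both totals from 9.2) it is 4.3%. Even an empty table bounds the risk.

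**The case against.** A reader might infer that STEPS events will be labelled Related far more often than identical control events, by three-fold or ten-fold. The documents do not support that. They set no window, and the ratio falls to 1.0 as the assumed window widens. The rule refers to study procedures, which both arms undergo, and 1.3 marks a control intervention over the same weeks as STEPS. Against that last point, 6.1.1 and 6.1.2 give controls only usual care, 6.4 collects no control adherence, and 8.1 defers their STEPS access until after the study. Counting usual care as a study procedure is therefore a strained reading, but the schedule leaves it open. The overlap also permits the Related label without forcing it. Inconsistency is shown; a directional bias is not.

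A reader might also infer that removals and unanticipated-problem reports would cluster in STEPS. Section 8.4.1 carries its own causation test and needs two further criteria, so a label based on timing does not trigger a report. Section 7.2 is discretionary and requires that the event warrant removal; relatedness alone is not sufficient. Recording (8.3.4) and reporting to the IRB, the funder and OHRP (8.3.5, 8.3.6) do not depend on the label.

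Nor do 8.3.4 and 10.1.6 conflict over who assesses. The first restricts causality to being "assessed only by those with the training and authority to make a diagnosis"; the second gives the PI overall responsibility. Both can hold.

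These points limit the consequences. They do not remove the overlap, the mismatch with 8.4.1, the conflict between AE definitions or the absence of any safety analysis.

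**Conclusion.** The point stands as a defect of definition together with a missing analysis. Followed exactly, 8.3.3.2 lets two assessors give opposite labels to one event: 6 of the 8 criterion combinations with a temporal relationship qualify for both. That result rests only on reading the two lists as they are joined, by or.

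A difference by arm is possible, because STEPS adds exposure over Day 8-91 and staff are unblinded. Its size cannot be derived. The range from 1.0 to about 10 shows how much depends on an unstated window; no value in it is an estimate.

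Because 8.3.1 conflicts with 8.2 and 8.3.4, and 9.4.4 plans nothing, the trial as planned will not compare harms between arms and cannot support from its own data the statement in 2.3.3 that risks are small. The change should be made. The primary efficacy analysis is not called into question by this point.

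**What to change.** 1. **8.3.3.2.** Define Related as a reasonable possibility that study procedures caused the event, in the terms of 8.4.1, and Not Related as everything else. Treat timing and alternate etiology as evidence weighed under that single test; neither should be sufficient alone.
2. **8.3.1.** Reconcile it with 8.2 and 8.3.4 so that AEs are counted regardless of relatedness. Without this step the table below could still be filtered by the label.
3. **9.4.4.** Replace N/A with the number and percentage of participants per arm with any AE, any SAE and any physical-activity injury, regardless of attribution, with 95% confidence intervals.

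The cost is protocol wording and one descriptive table. Section 8.3.4 already puts all AEs on the CRF, so no new data collection is needed, provided that events were recorded under that section and not screened out under 8.3.1. The downside is that some events now labelled Related would no longer be.

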8.3.3.3 EXPECTEDNESS

A member of the research team with appropriate expertise will be responsible for determining whether an adverse event (AE) is expected or unexpected. An AE will be considered unexpected if the nature, severity, or frequency of the event is not consistent with the risk information previously described for the study procedures.

8.3.4 TIME PERIOD AND FREQUENCY FOR EVENT ASSESSMENT AND FOLLOW-UP

The occurrence of an adverse event (AE) or serious adverse event (SAE) may come to the attention of study personnel during study appointments.

All AEs, not otherwise precluded per the protocol, will be captured on the appropriate case report form (CRF). Information to be collected includes event description, time of onset, assessment of severity,

relationship to study procedures (assessed only by those with the training and authority to make a diagnosis), and time of resolution/stabilization of the event. All AEs occurring while on study will be documented appropriately regardless of relationship. All AEs will be followed to adequate resolution.

Any medical or psychiatric condition that is present at the time that the participant is screened will be considered as baseline and not reported as an AE. However, if the study participant's condition deteriorates at any time during the study, it will be recorded as an AE.

Changes in the severity of an AE will be documented to allow an assessment of the duration of the event at each level of severity to be performed. Documentation of onset and duration of each episode will be maintained for AEs characterized as intermittent.

The study coordinator will record events with start dates occurring any time after informed consent is obtained until 7 (for non-serious AEs) or 30 days (for SAEs) after the last day of study participation. At each study visit, the investigator will inquire about the occurrence of AE/SAEs since the last visit. Events will be followed for outcome information until resolution or stabilization.

8.3.5 ADVERSE EVENT REPORTING

Any AE or SAE, whether or not related to study intervention, will be reported to the IRB, NCI, and the Office for Human Research Protections (OHRP). SAE's will be reported to the IRB within 24 hours and AEs will be reported to the IRB within 72 hours. All SAE's and AE's will be reported to NCI and OHRP within two weeks. The initial report will be followed by submission of a completed report to all institutions.

8.3.6 SERIOUS ADVERSE EVENT REPORTING

Any AE or SAE, whether or not related to study intervention, will be reported to the IRB, NCI, and the Office for Human Research Protections (OHRP). SAE's will be reported to the IRB within 24 hours and AEs will be reported to the IRB within 72 hours. All SAE's and AE's will be reported to NCI and OHRP within two weeks. The initial report will be followed by submission of a completed report to all institutions.

8.3.7 REPORTING EVENTS TO PARTICIPANTS

N/A

8.3.8 EVENTS OF SPECIAL INTEREST

N/A

8.3.9 REPORTING OF PREGNANCY

N/A

8.4 UNANTICIPATED PROBLEMS

No text is to be entered in this section; rather it should be included under the relevant subheadings below.

8.4.1 DEFINITION OF UNANTICIPATED PROBLEMS

This protocol uses the definition of Unanticipated Problems as defined by the Office for Human Research Protections (OHRP). OHRP considers unanticipated problems involving risks to participants or others to include, in general, any incident, experience, or outcome that meets all of the following criteria:

- Unexpected in terms of nature, severity, or frequency given (a) the research procedures that are described in the protocol-related documents, such as the Institutional Review Board (IRB)-approved research protocol and informed consent document; and (b) the characteristics of the participant population being studied;
- Related or possibly related to participation in the research (“possibly related” means there is a reasonable possibility that the incident, experience, or outcome may have been caused by the procedures involved in the research); and
- Suggests that the research places participants or others at a greater risk of harm (including physical, psychological, economic, or social harm) than was previously known or recognized.

8.4.2 UNANTICIPATED PROBLEMS REPORTING

The investigator will report unanticipated problems (UPs) to the reviewing Institutional Review Board (IRB). The UP report will include the following information:

- Protocol identifying information: protocol title and number, PI’s name, and the IRB project number
- A detailed description of the event, incident, experience, or outcome
- An explanation of the basis for determining that the event, incident, experience, or outcome represents an UP
- A description of any changes to the protocol or other corrective actions that have been taken or are proposed in response to the UP

To satisfy the requirement for prompt reporting, UPs will be reported using the following timeline:

- UPs that are serious adverse events (SAEs) will be reported to the IRB within 24 hours and to the funding agency within two weeks of the investigator becoming aware of the event

- Any other UP will be reported to the IRB within 72 hours and to the funding agency within two weeks of the investigator becoming aware of the problem
- All UPs should be reported to appropriate institutional officials (as required by an institution's written reporting procedures), the supporting agency head (or designee), and the Office for Human Research Protections (OHRP) within two weeks of the IRB's receipt of the report of the problem from the investigator.

8.4.3 REPORTING UNANTICIPATED PROBLEMS TO PARTICIPANTS

N/A

9 STATISTICAL CONSIDERATIONS

No text is to be entered in this section; rather it should be included under the relevant subheadings below.

9.1 STATISTICAL HYPOTHESES

- Primary Endpoint(s):

We hypothesize that, compared to participants who receive usual care, participants who receive the tailored mobile web-app, STEPS, will have a higher percentage of weight loss at 6 months post-randomization. Alternatively, our null hypothesis is that there will be no difference between arms in screening completion at 6 months.

- Secondary Endpoint(s):

A1C (3 and 6 months):

We hypothesize that the intervention arm will report a lower A1C at 3 and 6 months than the control arm; the null hypothesis is that there will be no difference between arms.

Diabetes Knowledge (3 and 6 months):

We hypothesize that the intervention arm will report higher diabetes knowledge (higher total score) at 3 and 6 months than the control arm; the null hypothesis is that there will be no difference between arms.

Eating Patterns (3 and 6 months):

We hypothesize that the intervention arm will report better eating patterns aligned with weight loss and management (total score) at 3 and 6 months than the control arm; the null hypothesis is that there will be no difference between arms.

Physical activity (3 and 6 months):

We hypothesize that the intervention arm will report higher amounts of physical activity at 3 and 6 months than the control arm; the null hypothesis is that there will be no difference between arms.

9.2 SAMPLE SIZE DETERMINATION

We examined power using treatment effects from two sources: 1) a meta-analysis examining the overall effectiveness of mobile device interventions on weight loss¹⁵⁴ and 2) a digital diabetes prevention program for low-income patients.⁸⁵ First, a meta-analysis examining the effects of mobile device interventions on weight loss found an average effect size of Cohen's d : 0.43 (95% CI:0.252-0.609; $p < 0.01$) across 11 mobile-based intervention studies.¹⁵⁴ This indicates an overall medium effect size. Second, Kim et al.⁸² developed and tested a mobile-based diabetes prevention program for a multi-racial/ethnic population. This study yielded a mean weight loss of 4.4% (SD 7.7%) at 12 months. This finding is associated with a Cohen's d =0.57, which is considered a medium effect size. To ensure our study is fully powered, we conducted our power analysis using the smaller effect size (Cohen's d =0.43) from Lyzwinski et al.¹⁵⁴, who examined the effects of mobile-based interventions on our primary outcome, participant weight loss.

We estimated power for the paired t-test for %weight loss (primary outcome). The G*Power 3.1 program¹⁵⁷ was used to determine that a Cohen's d of 0.43 and an α error probability of 0.05 requires a final sample size of 136 to be sufficiently powered ($1 - \beta$ error probability) at 0.80. Presuming a 20% attrition rate, randomizing a final sample size of 164 participants should be sufficient to detect significant differences in % weight loss across the two survey time points (i.e., at baseline and 3 months after the end of the intervention).

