6.3 MEASURES TO MINIMIZE BIAS: RANDOMIZATION AND BLINDING

Participants will be assigned to conditions by an algorithm programmed into the computer-based research portal. Randomization will utilize a permuted-blocks randomization scheme. Blocks of size 4 and 6 will be used. Assignments within blocks will be random but balanced among the two conditions and the order of the blocks (4 vs 6) also will be random. This procedure will ensure that the number of participants randomized to each condition will be equal, that any imbalance among the conditions at any point during the recruitment and randomization will be modest, and that it will be very difficult to guess the assignment of the next participant. Because the intervention and control materials are inherently different, participants and research staff cannot be blinded to assignment.

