9.4.2 ANALYSIS OF THE PRIMARY ENDPOINT(S)

The primary outcome is percent weight loss, and secondary outcomes include: HbA1c levels, diabetes knowledge, dietary intake, and self-reported physical activity. All but the weight and HbA1C measures (assessed by the research coordinator) will be self-reports using established scales that have evidence of reliability (internal consistency and/or a test-retest reliability) and validity. A paired t-test will be the main analytic technique for the primary measure (percent weight loss) and all continuous outcome measures. The test of the intervention effect will be the t-test for the regression coefficient for condition, which will estimate the adjusted difference between the two conditions at posttest. That test will be two-tailed with a type I error rate of 5%. Chi-square tests will be used for all categorical outcome data. We will perform the analysis using SAS PROC GLM, Version 9.1.¹⁴⁸ We will perform these analyses in collaboration with our statistical consultant, [name].

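### The 136 participants in Section 9.2 fit neither the paired t-test named there nor the two-tailed between-arm test in Section 9.4; for the latter, without covariate gain, power is about 69% to 78%, not 80%

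*Combined protocol and SAP*

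**What the plan says.** Section 9.2 (Sample Size Determination) names the test: "We estimated power for the paired t-test for %weight loss (primary outcome"). It takes the effect from a meta-analysis of mobile-device weight-loss interventions: "we conducted our power analysis using the smaller effect size (Cohen's d =0.43"). The other inputs are "an α error probability of 0.05" and power "error probability) at 0.80". Its result is that this "requires a final sample size of 136 to be sufficiently powered". It then presumes 20% attrition and randomises 164; Section 2.1 gives 165. Section 9.2 does not say whether alpha is one- or two-sided.

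Sections 9.4.1, 9.4.2 and 9.4.3 carry the same analysis text. Each first calls a paired t-test the main technique for the primary measure. Each then says: "The test of the intervention effect will be the t-test for the regression coefficient for condition", estimating an adjusted difference between the two conditions at posttest. On sidedness: "That test will be two-tailed with a type I error rate of 5" percent. Section 9.1 states the primary hypothesis as a difference between arms in percent weight loss at 6 months. Allocation is 1:1 in permuted blocks (Section 6.3): "Assignments within blocks will be random but balanced among the two conditions".

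Section 9.3 includes all randomised participants, expects very little missing primary-outcome data and plans imputation.

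**The concern.** A sample size should be reproducible from the test it is stated for. A paired t-test on 136 people at d = 0.43 has power of about 0.999, so 136 cannot be the number that test needs for 80%. A paired test also compares measurements within people, while the trial's question is whether the two arms differ.

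The between-arm test in Section 9.4 is two-tailed, and 136 is too few for 80% power under it. The 80% is the figure against which a null primary result would be read. With 136 analysed and a true d of 0.43, the chance of missing the effect is about 30% rather than 20%. With all 164 analysed it is about 22%.

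**Working it through.** **Inputs.** d = 0.43, alpha = 0.05, target power 0.80, 136 analysable, 20% attrition and 164 randomised (Section 9.2); 1:1 allocation (Section 6.3); two-tailed 5% test of condition (Sections 9.4.1 to 9.4.3). No covariate correlation is given, so the main figures assume no gain from adjustment.

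**Formulas.** Power comes from the noncentral t distribution.
- Two-sample: df = n1 + n2 - 2, noncentrality = d x sqrt(n1 x n2/(n1 + n2)).
- Paired: df = n - 1, noncentrality = d x sqrt(n).
- The critical value is the t quantile at 1 - 0.05 (one-sided) or 1 - 0.025 (two-sided).

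**Step 1: reproduce 136.** Smallest size with power of at least 0.80 at d = 0.43:

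| Test | Size needed | Power |
|---|---|---|
| Paired, two-sided | 45 | 0.805 |
| Paired, one-sided | 35 | 0.802 |
| Two-sample, two-sided | 86 per arm = 172 | 0.801 |
| Two-sample, one-sided | 68 per arm = 136 | 0.802 |

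For the last row, noncentrality = 0.43 x sqrt(68 x 68/136) = 0.43 x 5.831 = 2.507, df = 134 and the critical value is 1.656. With 67 per arm, power is 0.797, so 68 is the exact minimum. Only this row gives 136.

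**Step 2: power of the two-tailed between-arm test at the plan's sizes.** With 68 per arm the noncentrality is still 2.507, but the critical value rises to 1.978.

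| Analysed | Two-sided power at d = 0.43 | d detectable with 80% power |
|---|---|---|
| 131 (66 + 65) | 0.685 | 0.493 |
| 136 (68 + 68) | 0.702 | 0.484 |
| 164 (82 + 82) | 0.781 | 0.440 |

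Using the 165 from Section 2.1 changes little: 0.784 with all analysed, and 0.689 with 165 x 0.80 = 132.

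**Step 3: attrition.** 136 x 1.2 = 163.2, which rounds up to 164. To keep 136 after losing 20%, the number randomised must be 136/(1 - 0.20) = 170. From 164, a 20% loss leaves 164 x 0.80 = 131.2, about 131.

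**Step 4: size needed for 80%.** 172 analysable, or 172/0.80 = 215 randomised at 20% attrition.

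**Step 5: sensitivity to adjustment.** If d is defined on the unadjusted SD and covariates correlate r with the outcome, the effective d is 0.43/sqrt(1 - r^2). These r values are assumptions, not figures from the plan.

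| r | 131 analysed | 136 analysed | 164 analysed |
|---|---|---|---|
| 0 | 0.685 | 0.702 | 0.781 |
| 0.3 | 0.726 | 0.742 | 0.818 |
| 0.5 | 0.805 | 0.820 | 0.885 |

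**The case against.** Four arguments can be made for the plan.

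- **Little data may be lost.** Section 9.3 analyses everyone randomised and expects few missing weights. A reader might infer that power is about 70% at most, or 69% at the planned size. The documents do not support that: 70% belongs to 136 analysed and 69% to 131, while 164 analysed gives 78%. This objection stands against the stronger reading. It does not rescue the 80%, since 78% is still short, and Section 9.2 itself presumes 20% attrition.
- **The planned test is adjusted.** If baseline covariates predict the outcome well, power rises, and at r = 0.5 it passes 80% at all three sizes. So no firm ceiling can be stated. But Section 9.2 claims no such gain and gives no correlation. Section 9.4.5 controls only for variables that differ between groups at p < .10, which is not a prespecified prognostic covariate.
- **The hypothesis is directional, so a one-sided calculation could be intended.** A reader might infer from the exact match that a one-sided design was chosen. Section 9.2 does not say so, and Sections 9.4.1 to 9.4.3 commit to a two-tailed test. The one-sided basis remains an inference, and the conclusion does not depend on it.
- **The paired t-test is also named in Section 9.4.** This is true, so the analysis text is itself mixed. But the same paragraphs assign the test of the intervention effect to the condition coefficient, and Section 9.1 frames the hypothesis between arms. A paired test would not explain 136 in any case.

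A reader might also convert d to percentage points with the SD of 7.7% in Section 9.2. That SD belongs to 12-month weight loss in another study, and the quoted d of 0.57 equals 4.4/7.7, a mean divided by its own SD. Nothing in the plan makes it the between-arm SD at 6 months, so no such conversion is offered here.

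**Conclusion.** The sample-size statement is wrong as written. The figure of 136 is not what a paired t-test needs (45 or 35), nor what the two-tailed between-arm test needs (172). Among the variants checked, it is matched only by a one-sided two-sample test.

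At d = 0.43, equal allocation, two-sided 5% and no covariate gain, power is about 69%, 70% or 78% with 131, 136 or 164 analysed. Under those assumptions 80% is not reached at any size the plan contemplates. Separately, 164 randomised does not leave 136 after 20% attrition.

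The noncentral-t arithmetic is firm. The one-sided origin of 136 and the 1.2 multiplier behind 164 are inferred from exact matches, and the effect of covariate adjustment cannot be fixed from the documents.

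**What to change.** Keep the sample size and make these changes:

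1. Rewrite Section 9.2 for the two-sided 5% between-arm comparison of 6-month percent weight loss.
2. Restate power at d = 0.43 as about 69% (131 analysed), 70% (136) and 78% (164). Equivalently, state 80% power for d of about 0.49, 0.48 and 0.44 respectively. Say that no covariate gain is assumed.
3. Correct the attrition statement: 164 randomised less 20% leaves about 131, and 136 analysable would need 170 randomised.
4. Remove the paired t-test as the test of the intervention effect in Section 9.2 and in Sections 9.4.1 to 9.4.3, so that the calculation and the analysis name one test.

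The cost is one rewritten paragraph in Section 9.2, a wording change repeated in three subsections and a less favourable stated power. No extra participants are needed.
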